7.4.4 Subgroup analyses

Subgroup variables will be explored as described in [Section 6.4](#) for the primary endpoint. The HR between the two treatments along with 95% CI and the p-value for test of treatment equality within each category of the subgroup as well as the p-value for the subgroup-by-treatment interaction will be estimated by the Cox proportional hazard model including the same covariates as in the primary analysis of primary endpoint, the subgroup variable if not part of the covariates of the primary analysis model, and subgroup-by-treatment interaction. If the subgroup variable is a categorization of a continuous covariate, this covariate will be dropped from the subgroup model. A forest plot will be presented with the estimated HR and the two-sided 95% CI for each subgroup category. The CIF plots will also be presented for each subgroup category.

For subgroup analyses of baseline LVEF and baseline uric acid, the interaction p-values will be calculated using trend tests, taking into account that the subgroup categorizations are ordered. Assuming the difference between the adjacent subgroup is the same, each subgroup is coded as numeric value ordinally and fitted into the model as numeric covariate. The model also includes terms of subgroup variable and subgroup-by-treatment interaction.

If there are less than 14 patients with events in one subgroup, then this subgroup will not be included in the model. If this leaves only one subgroup, the subgroup analysis will not be conducted.

For the continuous covariates baseline LVEF, baseline eGFR and age, the influence of the covariate will also be investigated on a continuous scale. For this purpose the continuous covariate will be added to the model if not already included and the interaction term of the continuous covariate and treatment will additionally be included into the model. The hazard ratio depending on the continuous covariate will be plotted and the interaction p-value will be reported.

7.5 SECONDARY ENDPOINTS

7.5.1 Key secondary endpoints

Occurrence of adjudicated HHF (first and recurrent)

Hospitalisation for heart failure will be analysed by a joint frailty model (JFM) that accounts for the dependence between recurrent HHF and CV death (7). The primary analysis will be based on all data available until completion of the planned treatment phase, including the data after end of treatment for patients not completing the treatment phase as planned.

Define $T_{i0} = 0$ and let $T_{i1}, T_{i2}, \dots, T_{iN_i}$ be the recurrent event times for person i , where N_i is the number of recurrent HHF events before $X_i = \min(C_i, D_i)$, the minimum of an independent censoring time C_i and a dependent CV death time D_i . The JFM is defined through the hazard functions for the recurrent event process and CV death

$$r_i(t | \omega_i) = \omega_i \exp\{\beta_1 z_i\} r_0(t)$$

$$\lambda_i(t | \omega_i) = \omega_i^\alpha \exp\{\beta_2 z_i\} \lambda_0(t)$$

The recurrent heart failure hospitalisations intensity function for the i -th patient conditional on the patient specific random frailty, ω_i , is given by r_i and is proportional to the baseline intensity function, r_0 . The conditional hazard function for time to CV death for patient i is given by λ_i , with the baseline hazard given by λ_0 , and β_1, β_2 are $p \times 1$ vectors of regression coefficients associated with vectors of covariates z_i . The same covariates as for the analysis of the primary endpoint will be used, e.g. β_1 =treatment (empagliflozin, placebo), β_2 =region (North America, Latin America, Europe, Asia and “other” including India, South Africa, and Australia), β_3 =baseline status of diabetes (diabetes, prediabetes, no diabetes) etc.

Patient specific independent random effects are denoted by ω_i and are assumed to follow a gamma distribution with mean 1 and variance θ . The correlation of the recurrent events is quantified by θ , with higher values corresponding to greater within-patient correlation and also greater between-patient variability. The parameter α determines the relationship between the recurrent heart failure hospitalisations and time to CV death. When $\alpha < 0$, higher frailty will result in a greater risk of recurrence and lower risk of terminal event (i.e. a negative

correlation between the frailties), and when $\alpha > 0$, higher frailty will result in a greater risk of recurrence and is associated with a higher risk of CV death (i.e. a positive correlation between the frailties).

Let t_{ij} and x_i be the observed recurrent event times and follow-up, respectively. Denote by δ_{ij} and Δ_i , the indicator of the recurrent event at time t_{ij} and the indicator of CV death at time x_i , respectively. The likelihood for person i is then given by the following:

$$L_i = \int_{\omega_i} \prod_{j=1}^{N_i} [\omega_i r_i(t_{ij})]^{\delta_{ij}} \exp \left\{ \int_0^{x_i} \omega_i r_i(t) dt \right\} [\omega_i^\alpha \lambda_i(x_i)]^{\Delta_i} \exp \left\{ \int_0^{x_i} \omega_i^\alpha \lambda_i(t) dt \right\} f_\theta(\omega_i) d\omega_i.$$

Adopting piecewise constant hazards for the recurrent events and CV death allows estimation of the likelihood by Gaussian quadrature. The implementation of the used adaptive Gaussian quadrature techniques is incorporated into Proc NLMIXED of SAS 9.4. SAS Code following the strategy outlined in (9) will be used.

The size of the pieces for the piecewise constant hazards can be different and are determined separately for the terminal as well as recurrent event process with 10 pieces each. The nodes are defined by the empirical deciles of the recurrent or terminal events, respectively.

The joint frailty model using the multiplicative parametrization with non-normal random effects will be fitted using a likelihood-reformulation method (10).

To improve convergence of the model, linear covariates (in case no interaction with treatment is modelled) will be standardized prior inclusion into the analysis and starting values for the model parameters will be determined using the following procedure:

- 1) An exponential model will be fitted for the terminal event and a poisson regression model for the recurrent event process including the same covariates that are included in the final joint frailty model to get initial starting values for all parameters.
- 2) A simplified model without random effect ω which is otherwise equal (regarding covariates, baseline hazards) to the joint frailty model is fitted using the values from step (1) as starting values for the parameters. The estimated coefficients from the simplified model will then be used as starting values for the parameters of the piecewise-constant joint frailty model.

The joint model gives two distinct hazard ratios:

$HR_{HHF} = \exp\{\beta_{11}\}$ is the hazard ratio associated with the effect of treatment on the recurrent event rate of HHF, and $HR_{CVD} = \exp\{\beta_{21}\}$ is the CV death hazard ratio.

Estimates and 95% CI for the hazard ratios and for α (relationship between the recurrent heart failure hospitalisations and CV death) will be given.

The following sensitivity analyses will be conducted

- Based on the TS, including only any events up to 30 days after treatment discontinuation
- Instead of CV-death, jointly model HHF with all-cause mortality as the terminal events (otherwise same model as initially described)

- The endpoint will be additionally evaluated based on investigator defined events for HHF and CV death (otherwise same as initially described model).
- A parametric joint gamma-frailty model will model the recurrent event component using a Poisson distribution and model the CV mortality component using an exponential distribution, conditional on the frailty parameter. Individual frailties are again assumed to follow a Gamma distribution. Thus HHF rates follow a negative binomial distribution and times to CV death follow a Lomax distribution (see [\(8\)](#)) (otherwise – e.g. covariates - same as initially described model).
- The analysis will be repeated to include all events up to individual trial completion including the follow-up period (otherwise same as initially described model).
- The analysis will be repeated to include only confirmed HHF which meet the CDISC guidance criteria for hospitalization for heart failure (i.e., confirmed by adjudication committee, but excluding those missing a physical sign or laboratory test, or both).
- The analysis will be repeated to include all events up to cutoff dates prior to COVID-19 outbreak – cutoff (censoring) dates are 30Nov2019 for China and 31Dec2019 for all other countries.
- The analysis will be repeated to include all events up to 7 days prior to a reported SARS-CoV-2 infection (based on broad scope SARS-CoV-2 infections)

In case the semi-parametric joint modelling cannot converge numerically with the existing SAS procedures, the parametric joint gamma-frailty model as described above may be used instead for the confirmatory analysis.

The number of HHF events per patient will be summarized descriptively. Additionally a negative binomial model will be fitted to the data of recurrent HHF. This will be done once including only treatment as covariate and once including all covariates as the primary model. Rate ratio and confidence intervals of both models will be reported.

The mean cumulative incidence will be displayed for adjudicated recurrent HHF.

Subgroup analyses will be explored as outlined in [Section 6.4](#) for adjudicated recurrent HHF. For subgroup analyses the term of subgroup (if not already part of the model) and subgroup by treatment will be added to the model of the recurrent event. If the subgroup variable is a categorization of a continuous covariate, this covariate will be dropped from the subgroup model.

eGFR (CKD-EPI)_{cr} slope of change from baseline

Slope in change from baseline of eGFR (CKD-EPI)_{cr} will be analysed by a random coefficient model allowing for random intercept and random slope per patient. The model will include the factors treatment, sex, geographical region, and status of DM as fixed effects and eGFR (CKD-EPI)_{cr} at baseline (continuous), LVEF (continuous), age (continuous), time and interaction of treatment by time and interaction of eGFR (CKD-EPI)_{cr} at baseline

(continuous) by time as linear covariates and allow for randomly varying slope and intercept between patients. The model will include all on-treatment change from baseline data.

Since the slope is run on the change from baseline data, the intercept will model the acute drop, whereas the long-term effect is modelled by the slope.

A plot of individual patient slopes and separately of individual patient intercepts will be provided per treatment and by eGFR at baseline.

Subgroup analyses as outlined in [Section 6.4](#) will be explored for eGFR slope. The subgroup model will include additionally to the model described above, the subgroup if not already part of the model, subgroup by treatment and subgroup by treatment by time. If the subgroup variable is a categorization of a continuous covariate, this covariate will be dropped from the subgroup model.

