6.4 SUBGROUPS

Subgroups to be considered in the analyses are provided below in [Table 6.4: 1](#). Missing categories for subgroup variables will not be considered in the respective analysis.

If there is missing information for any of the subgroups, where data is also collected in the IRT system, then the information as transferred from IRT will be used to assign a patient to a certain category.

Although several subgroup analyses are prespecified in [Table 6.4: 1](#), the subgroup analysis by Diabetes at baseline (diabetic, non-diabetic) is the medically and academically most important subgroup analysis.

Table 6.4: 1 Categories of covariates for displays of baseline characteristics and subgroup analyses

Variable	Categorization	Demo-graphics ¹	Subgroups for Efficacy endpoints ²	Safety ³
Diabetes at baseline	diabetic, non-diabetic	X	X	X (except ketoacidosis and hypoglycaemia)
	non-diabetic (Pre-diabetes, normal (no pre-diabetes)), diabetic (type 2 diabetes, type 1 diabetes)	X		X (Ketoacidosis and hypoglycaemia)
Age (years)	<50 50 to <65 65 to <75 75 to <85 ≥ 85	X		X
	< 70 ≥70	X	X	
Sex	male female	X	X	X
Region	NA, LA, Europe, Asia, Other ⁺	X		X (overall ⁴ only)
Ethnicity	Hispanic/ Latino Not Hispanic/ Latino	X		X (overall ⁴ only)
Race ^s	White Black/ African-American Asian Other including mixed race	X	X	X
BMI (kg/m ²)	<30 ≥30	X	X	
eGFR at baseline	≥90 60 to <90 45 to <60 30 to <45 20 to <30 <20	X		
	≥90 60 to <90 45 to <60 30 to <45 <30	X		X
	≥60 <60	X	X	

Table 6.4: 1 Categories of covariates for displays of baseline characteristics and subgroup analyses (cont.)

Variable	Categorization	Demo- graphics ¹	Subgroups for Efficacy endpoints ²	Safety ³
UACR	UACR (in mg/g): <30 >=30 to <=300 >300	X		
Baseline SBP	< / >= median		X	
Baseline BP	SBP<140 and DBP<90 vs. SBP>= 140 or DBP>=90	X		X (volume depletion AEs and hypotension AEs)
History of Atrial Fibrillation or Atrial Flutter ^{SS}	Yes/ No	X	X	
Baseline LVEF	</>=50	X		
	<50, 50 to <60, >=60	X	X	
History of HHF (in the last 12 months)	Yes / No	X	X	
Time since diagnosis of HF	<= 1 year, 1-5 years, > 5 - 10 years, >10 years	X		
NYHA at baseline	I/II/III/IV	X		
	II vs. III/IV		X	
NT-proBNP	< / >= median (calculated separately for patients with/without history of atrial fibrillation or atrial flutter ^{SS})		X	
Baseline uric acid	Tertiles (calculated separately for males and females)	X	X	
Baseline use of ACE- inhibitor, ARB or ARNi	Yes / No	X#	X	X (renal AEs, volume depletion AEs and hypotension AEs)

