Baseline use of MRA	Yes / No	X#	X	

Table 6.4: 1 Categories of covariates for displays of baseline characteristics and subgroup analyses (cont.)

Variable	Categorization	Demo-graphics ¹	Subgroups for Efficacy endpoints ²	Safety ³
Baseline use of diuretics	Yes / No	X#		X (renal AEs, volume depletion AEs and hypotension AEs)
Baseline use of loop or high-ceiling diuretics	Yes / No	X#		X (renal AEs, volume depletion AEs and hypotension AEs)

¹ The column demographics shows categories shown in the overall demographics.

Demographics are not planned by subgroup.

² Subgroups planned for the primary endpoint, time to cardiovascular (CV) death, time to first HHF, HHF (first and recurrent), renal slope.

³ X means subgroups planned for overall AE summaries, AEs by SOC and PT, SAEs, AEs leading to discontinuation, decreased renal function, UTI, genital infection, volume depletion, hypotension and bone fracture.

⁴ Overall means overall AE summaries, AEs by SOC and PT, SAEs and AEs leading to discontinuation

⁵ Median calculated separately for baseline atrial fibrillation or atrial flutter (determined by ECG) / no baseline atrial fibrillation and atrial flutter (determined by ECG)

⁺ Region categorization: see [Table 9.1.1](#).

[#] part of the presentation of baseline concomitant therapy as outlined in [Section 7.2](#)

[§] Due to low number of patients in certain race categories, estimates for race subgroups may be unstable.

^{§§} history of atrial fibrillation or atrial flutter means atrial fibrillation or atrial flutter reported in any ECG before treatment intake or history of atrial fibrillation or atrial flutter reported as medical history.

Additional subgroup analyses for specific further endpoints are defined in [Section 7.6](#)

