7.4.1 Primary analysis of the primary endpoint(s)

As the primary endpoint, time to the first event of adjudicated HHF or adjudicated CV death will be reported in days. The primary analysis will be based on RS, using all data available until completion of the planned treatment phase, including the data after end of treatment for patients not completing the treatment phase as planned.

The primary endpoint will be displayed using cumulative incidence function (CIF) curves and expressed as the hazard ratio with associated two-sided 95% confidence intervals (CIs) and two-sided CIs based available alpha-level for the analysis.

For the interim analysis and final analysis, the following Hwang, Shih and De Cani α -spending function at information fraction t_k with parameter $\gamma = -8$ will be used:

$$\alpha^*(\gamma, t_k) = \min \left\{ \alpha, \quad \alpha \frac{1 - e^{-\gamma t_k}}{1 - e^{-\gamma}} \right\} = \min \left\{ 0.025, \quad 0.025 \frac{1 - e^{8t_k}}{1 - e^8} \right\}$$

The alpha levels are expected to be 0.001 and 0.0248 (one-sided) for the interim and final tests respectively, when the interim analysis occurs at the time of 60% information.

Estimator and corresponding confidence intervals will not be corrected for interim analysis.

The primary endpoint will be analysed using Cox regression, with factors of treatment (empagliflozin, placebo), region (North America, Latin America, Europe, Asia and “other” including India, South Africa and Australia), baseline status of diabetes (diabetes, prediabetes, no diabetes), age (continuous), sex, left ventricular ejection fraction (LVEF) (continuous) and eGFR (CKD-EPI)_{cr} at baseline (continuous). Since the stratification factors are included in the model as covariates, no stratified Cox regression will be used.

Breslow’s method will be used for dealing with ties.

The individual relevant components of the composite will be summarized descriptively. In this descriptive analysis of the relevant component for the composite, CV death after HHF will not be counted. In all other analyses of CV death alone defined in this document, all CV deaths will be counted, disregarding any earlier events.

A hierarchical testing procedure will be followed for the assessment of the primary and key secondary endpoints. For all endpoints, superiority of empagliflozin vs. placebo will be evaluated using a two-sided test.

The tests will be performed in the following hierarchical order:

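### The recurrent-HHF subgroup models put the treatment interaction only in the HHF hazard, so a real CV-death interaction can leak, reversed, into the HHF result

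*SAP*

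**What the plan says.** Section 7.5.1 of the current SAP (revised 12-FEB-2021) defines two hazards for each patient, one for recurrent HHF and one for CV death. They share a gamma frailty with variance θ. "The parameter α determines the relationship between the recurrent heart failure hospitalisations and time to CV death". Each hazard has its own coefficients: β1 and β2 are "vectors of regression coefficients associated with vectors of covariates z_i". On content, "The same covariates as for the analysis of the primary endpoint will be used". Section 7.4.1 lists these as treatment, region, diabetes status, "age (continuous), sex, left ventricular ejection fraction (LVEF) (continuous) and eGFR (CKD-EPI)_{cr} at baseline (continuous").

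For subgroups, section 7.5.1 states that the subgroup term (if not already present) and "subgroup by treatment will be added to the model of the recurrent event". It continues: "If the subgroup variable is a categorization of a continuous covariate, this covariate will be dropped from the subgroup model".

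Footnote 2 to Table 6.4:1 sets the scope: "Subgroups planned for the primary endpoint, time to cardiovascular (CV) death, time to first HHF, HHF (first and recurrent), renal slope". The efficacy subgroups include age (below 70, or 70 and over), eGFR (below 60, or 60 and over) and LVEF ("<50, 50 to <60, >=60"). Section 6.4 names diabetes at baseline as the most important subgroup analysis. Section 9.4 adds USA versus non-USA, region, ethnicity and a five-category eGFR split for the same endpoints.

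**The concern.** The joint model is used because HHF and CV death are dependent. In the subgroup version only the HHF hazard may have a treatment effect that varies by subgroup.

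Suppose treatment lowers CV death in one subgroup but not in the other. A CV-death part with a common effect then expects too many deaths among treated patients in the first subgroup. The model accounts for the shortfall by inferring lower frailty there. The same frailty multiplies the HHF rate, so the observed hospitalisations have to be explained by a worse HHF hazard ratio in that subgroup. The reverse happens in the other subgroup. The HHF interaction is thus pushed against the direction of the CV-death interaction.

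At stake are the subgroup-specific HHF hazard ratios and interaction p-values for the first key secondary endpoint. They could suggest effect modification on HHF that comes from CV death. This applies to every subgroup, diabetes included, because a covariate that stays in the CV-death part as a main effect still has no treatment interaction there.

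**Working it through.** **What the text fixes.** The SAP gives no figure for the subgroup joint model, so there is none to reproduce. As a check of scale, the primary event count does reproduce: 4(1.960 + 1.282)² / (ln 0.80)² ≈ 844, or 845 after rounding up, against the stated 841. Power at 841 events is 89.9%. The planned size of about 5750 patients (section 9.6) is used below.

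**Model fitted.** With T = treatment and S = subgroup:

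- HHF: r = ω · r₀ · exp(b₁T + b₂S + b₃TS)
- CV death, terms in both parts: λ = ω^α · λ₀ · exp(d₁T + d₂S + d₃TS)
- CV death, literal SAP reading with the covariate also lost: λ = ω^α · λ₀ · exp(d₁T)

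Fitting was by maximum likelihood with quadrature over a gamma frailty, with constant baseline hazards in place of the SAP's ten pieces.

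**Assumptions not in the SAP.** HHF rate 0.10 per year and CV-death rate 0.04 per year at frailty 1; follow-up of 1.2 to 3.2 years; equal-sized subgroups; HHF hazard ratio 0.75 in both subgroups, so the true b₃ is 0; θ, α and CV-death hazard ratios as shown.

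**Results, one data set of 60,000 patients per row, both models fitted to the same data.** Shift = b₃ with terms in the HHF part only, minus b₃ with terms in both. The SE is rescaled to 5750 patients by √(60000/5750) = 3.23.

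| θ, α | CV-death HR in S=0 / S=1 | S main effect on CV death | b₃, both parts | b₃, HHF part only | Shift | exp(shift) | Shift / SE |
|---|---|---|---|---|---|---|---|
| 4, 0.8 | 0.6 / 1.2 | none | −0.058 | −0.188 | −0.130 | 0.88 | 0.130/0.164 = 0.8 |
| 4, 0.8 | 0.8 / 1.0 | none | 0.079 | 0.034 | −0.045 | 0.96 | 0.045/0.163 = 0.3 |
| 2, 0.5 | 0.6 / 1.2 | none | 0.053 | 0.006 | −0.047 | 0.95 | 0.047/0.145 = 0.3 |
| 4, 0.8 | 0.6 / 1.2 | HR 2 | 0.011 | −0.153 | −0.164 | 0.85 | 0.164/0.164 = 1.0 |
| 8, 1 | 0.6 / 1.2 | none | −0.047 | −0.295 | −0.248 | 0.78 | 0.248/0.190 = 1.3 |
| 4, 0.8 | 0.9 / 0.9 | HR 2 | −0.022 | 0.004 | +0.026 | 1.03 | 0.026/0.166 = 0.2 |

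The individual b₃ values carry sampling noise, most of which cancels in the paired shift.

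**Which omission matters.** Keeping the S main effect in the CV-death part and leaving out only the interaction gives shifts of −0.135 in the first row and −0.164 in the fourth, practically the same as leaving out both. In the last row there is no CV-death interaction, and losing a strong prognostic main effect moves b₃ by only +0.026. A further fit (θ 3, α 1, log hazard ratio of S on death 1.0, no interaction) moved it by −0.001. The missing interaction is the cause.

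**At the planned size.** 66 simulated trials of 5750 patients in the first row's setting:

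- Terms in both parts: mean b₃ −0.004 (Monte Carlo SE 0.021); interaction test below 0.05 in 6%.
- HHF part only: mean b₃ −0.132; interaction test below 0.05 in 18%.
- Paired shift −0.128 (Monte Carlo SE 0.007); exp(−0.128) = 0.88.

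The 18% rests on 66 runs; a normal approximation with a 0.8 SE shift gives about 12%.

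**Lower end.** With θ 1, α 0.8 and a CV-death log interaction of 0.25 the shift was −0.004. With θ 3, α 1 and 0.4, separate fits gave about −0.09 and −0.12.

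**The case against.** The wording can be read more kindly. If the model of the recurrent event is loose wording for the whole joint model, the terms enter both hazards through the common covariate vector and nothing is wrong. That reading is possible. However, section 7.5.1 elsewhere separates the recurrent from the terminal process, so the phrase more naturally names one part, and nothing else in the SAP puts these terms in the CV-death hazard.

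A reader might infer that age, eGFR or LVEF certainly disappear from the CV-death part, and that this distorts the HHF result. The documents do not support either step. The disappearance needs one sentence to mean the HHF part and the next to mean the whole model. If both mean the HHF part, the continuous covariate stays in the CV-death hazard. And the loss of a main effect alone hardly moves the HHF interaction.

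The size rests on assumed values. Hazard ratios of 0.6 and 1.2 are a reversal of effect on CV death; at 0.8 and 1.0 the shift is about 0.3 standard errors. CV death is also analysed in the same subgroups, so a strong interaction there would be looked for directly. This limits the harm, but the HHF estimates remain biased.

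Parsimony is a fair motive: there are ten pieces per hazard, special starting values and a fallback for non-convergence. The SAP does not give it as the reason.

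**Conclusion.** The point holds in a limited form. Read literally, the subgroup joint model forces a common treatment effect on CV death. If that effect truly differs by subgroup, the HHF interaction and the subgroup HHF hazard ratios are biased in the opposite direction. The bias ranges from near zero, with a weak frailty link or a small CV-death interaction, to about 12% on the interaction ratio, or about 0.8 standard errors at 5750 patients, with a strong one. More extreme assumed settings went further (15% and 22% in the table), but the conclusion does not rest on them. All sizes depend on θ, α and a CV-death interaction that the SAP does not give, and on a simplified baseline hazard.

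A reader might also infer that the key secondary test is compromised. It is not: the subgroup analyses are exploratory and the confirmatory model contains no subgroup interaction. The possible loss of age, eGFR or LVEF from the CV-death part is an ambiguity worth closing, with little effect of its own on the HHF interaction. This is a minor improvement, worth making because it is cheap.

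**What to change.** In section 7.5.1, state that the subgroup (if not already in the model) and subgroup-by-treatment terms are added to both the recurrent-HHF and the CV-death hazards. State also that a continuous covariate is dropped only from a hazard in which its categorised form replaces it. If the model does not converge in a sparse subgroup, fall back to terms in the recurrent-event hazard only and label that result as such.

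In the setting tested at 5750 patients, terms in both hazards removed the bias (mean log ratio −0.004). The cost is a few more parameters per model, slightly longer run time and a small added risk of non-convergence. The precision lost is small: the average standard error of the interaction rose from 0.165 to 0.171.
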